1 SYNOPSIS

Study Synopsis	
Title	PREVENT ion of Non-Surgical Bleeding by Management of HeartMate II Patients without Antiplatelet Therapy
Acronym	PREVENT II
Objectives	Reduce the incidence of non-surgical bleeding in HeartMate II (HM II) patients without increasing the risk of thromboembolic (TE) events
Primary Hypothesis	HM II patients managed with warfarin alone (Treatment Arm) have a lower rate of non-surgical bleeding and an equivalent rate of stroke and TE events compared to patients managed with warfarin + acetylsalicylic acid (aspirin, ASA) together (Control Arm)
Primary Endpoints	
A comparison between the Treatment and Control Arms of:
 
Primary Efficacy Endpoint (Superiority): Composite incidence of non-surgical bleeding at 6 months post initial implantation, including but not limited to gastrointestinal (GI), genitourinary (GU), epistaxis, subdural hematoma, and primary hemorrhagic stroke (not due to ischemic conversion, or to treatment of a hemolysis/suspected thrombosis event)
 
Primary Safety Endpoint (Non-Inferiority): Composite incidence of pump thrombosis and TE stroke at 6 months post initial implantation, including ischemic stroke, or hemorrhagic stroke due to an ischemic conversion/treatment of an hemolysis/pump thrombosis event

Descriptive Endpoints	
Comparison between the Treatment and Control Arms in the rates of:
 
 • Overall bleeding • GI bleeding • Suspected and confirmed pump thrombosis • Stroke (ischemic and hemorrhagic) • Hemolysis (major and minor) • As treated analysis of anticoagulation and antiplatelet medications • Survival • Assessment of adherence to the PREVENT study recommended practices

Clinical Investigational Plan

Study Synopsis

Design

PREVENT II is a prospective, multi-center, randomized, double-blind placebo controlled study.

The randomization scheme will be 1:1, with a total sample size of 350 subjects, with 175 subjects in the Treatment Arm and 175 subjects in the Control Arm defined as:

- Treatment Arm: Warfarin (INR Target 2.0-2.5, median 2.25, per standard of patient care) + placebo (1 pill/day)
- Control Arm: Warfarin (INR Target 2.0-2.5, median 2.25, per standard of patient care) + acetylsalicylic acid (ASA) therapy (81mg/day)

Maximum follow-up duration per subject will be 12 months. Primary endpoints will be evaluated at 6 months. Individual components of the primary endpoints along with the descriptive endpoints will be evaluated at 12 months.

Clinical Investigational Plan

Study Synopsis

Statistical Considerations	
Primary Efficacy Endpoint Analysis – Reduction of Bleeding: The rate of non-surgical bleeding at 6 months will be compared between the Treatment and Control Arms utilizing the Fisher’s Exact Test. The primary endpoint for efficacy will be assumed to be met if the p-value < 0.05. The assumption is that there will be a 15% rate reduction at 6 months.
 
A sample size of 330 subjects (165 in each arm) with an alpha of 0.05 will provide 80% power to demonstrate a significant difference between the Treatment and Control Arms.
 
Primary Safety Endpoint Analysis – Non-Inferiority of Stroke and Thrombus: The difference in the rates of the composite endpoint of stroke and pump thrombosis between Treatment and Control Arms and the 95% confidence limit of the difference will be evaluated. If the upper confidence limit of the difference is < 10% then the non-inferiority criterion will be considered to have been met.
 
A sample size of 338 subjects (169 in each arm) will provide 80% power, with a target alpha of 0.025 (because this will be a one-sided test on the upper confidence limit) to demonstrate non-inferiority of the Treatment Arm to the Control Arm.
 
A total study sample size of 350 subjects will provide enough statistical power to demonstrate both efficacy and safety of the warfarin only anticoagulation regimen in these patients.
 
Both primary endpoints must be met for the study to be successful.
 
Intermediate Safety Assessment: A safety assessment will be performed after 60 subjects have completed 3 months of follow-up. Both incidence of stroke and pump thrombosis will be analyzed and results will be presented to the Steering Committee. Additionally, after the initial 3-month safety review, an analysis of AEs associated with primary endpoints will be presented to the Steering Committee for continued safety assessment in regular 6-month intervals. The Steering Committee will review the findings and make a decision to proceed or stop the study due to safety concerns.

Devices Used	HM II Left Ventricular Assist Device (LVAD)
Research Drug	Aspirin (81mg – active ingredient: Acetylsalicylic acid (ASA); Enteric-Coated Low Dose Aspirin, Bayer Corporation, Whippany, NJ) will be blinded to a matching placebo (ALMAC Clinical Services, Souderton, PA)
Study Population	All patients undergoing HM II implantation per approved indications who meet inclusion/exclusion criteria may be considered for this study.

Clinical Investigational Plan

Study Synopsis

Inclusion & Exclusion Criteria	
Inclusion Criteria
 
 • Subject is receiving the HM II per standard of care (SOC) in accordance with the approved indications for use • Subject is ≥ 50 years of age • Subject is receiving the HM II as their first LVAD • Subject or legally authorized representative (LAR) has signed an informed consent form (ICF). 
Exclusion Criteria
 
 • Existence of ongoing mechanical circulatory support (MCS) other than intra-aortic balloon pump or Abiomed Impella® devices • Participation in any other clinical investigation(s) involving an MCS device, or an investigation(s) that is likely to confound study results or affect study outcome • Antiplatelet therapy is mandated for other conditions, in particular: a) recent coronary artery stenting (≤ 6 months), b) carotid artery disease, and c) other conditions where the investigator is not comfortable leaving subjects off-ASA or starting ASA post LVAD implantation. In situations where the investigator is uncertain, the Steering Committee can provide a recommendation to the investigator as needed. • Subjects in whom heart transplantation is expected in ≤ 6 months • Subjects with a known ASA allergy
Data Collection	
Data will be collected on all subjects at the following time points:
 
 • Baseline • Implant • Week 1 post-implant (± 3 days) • Month 1 post-implant (± 7 days) • Month 3 post-implant (± 20 days) • Month 6 post-implant (± 20 days) • Month 9 post-implant (± 20 days) • Month 12 post-implant (± 20 days) 
Data will be collected for as occurs events, including initial discharge, adverse events, re-hospitalizations, operative events and outcomes. All changes to anticoagulant and antiplatelet therapies and all available values for INR and LDH will be collected during the follow-up period.

Clinical Investigational Plan**2 BACKGROUND AND JUSTIFICATION FOR CLINICAL STUDY**

Over the last decade, mechanical circulatory support (MCS) with continuous-flow (CF) left ventricular assist devices (LVADs) has become the standard of care (SOC) treatment for patients with advanced stage heart failure. The HeartMate® II (HM II) LVAD is a commercially available, U.S. Food and Drug Administration (FDA) and Health Canada approved device. The HM II was approved for New York Heart Association Class (NYHA) III/IV patients as a bridge to cardiac transplantation (BTT) by the FDA in April 2008 and Health Canada in May 2009. The HMII was approved for permanent destination therapy (DT) by the FDA in January 2010 and Health Canada in October 2010. Numerous publications have documented the success of the HM II in extending and improving the quality of life in patients with advanced heart failure (1-10). Over 22,000 patients have been implanted and treated with the HM II LVAD, and over 8,000 patients are currently supported by the HM II (*data on file*).

Patients with LVADs require adjunctive antithrombotic therapy, typically with warfarin +/- acetylsalicylic acid (aspirin, ASA). While ASA therapy, the research topic of this study, is suggested in the HM II IFU, the usage of ASA as SOC is variable. Some centers routinely utilize ASA while others do not (11, 12). Additionally, ASA therapy is usually discontinued when patients experience a serious bleeding event (13).

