4.2 STUDY DESIGN AND SCOPE

This study is a prospective, multi-center, randomized, double-blind placebo-controlled study of subjects receiving the HM II LVAD as per currently approved indications for use. This is a post-market clinical study of HM II patient management practices to be conducted in the United States and Canada.

Subjects will be randomized in a 1:1 fashion to the following research drug groups:

- 1) Treatment Arm: Warfarin (INR target: 2.0-2.5, median: 2.25) + Placebo (1 pill/day)
- 2) Control Arm: Warfarin (INR target: 2.0-2.5, median: 2.25) + ASA Therapy (81mg/day)

The study will investigate if subjects in the Treatment Arm experience a reduced incidence of non-surgical bleeding, without an increased risk of TE events.

Once randomized, subjects will be placed on the research drug (ASA therapy or placebo) no later than post-operative day (POD) 5, provided bleeding has subsided and the subject is hemodynamically stable.

If the subject is experiencing bleeding or is not hemodynamically stable by POD 5, the subject must start the study drug as soon as bleeding has subsided and hemodynamic stability has been achieved, but no later than POD 15. If administration of the research drug has not begun by POD 15, the subject will be withdrawn from the study.

Withdrawn subjects will not be replaced.

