12 STATISTICAL CONSIDERATIONS

PREVENT II is a prospective, multi-center, randomized, double-blinded, placebo-controlled study evaluating the risk of subjects over 50 years of age being managed on warfarin therapy alone compared to warfarin and ASA therapy together. The two groups in the study are as follows:

- 1) Treatment Arm: Warfarin (INR target: 2.0-2.5, median: 2.25) + Placebo (1 pill/day)
- 2) Control Arm: Warfarin (INR target: 2.0-2.5, median: 2.25) + ASA therapy (81mg/day)

In general, continuous data will be presented as the number of subjects, mean with standard deviation, median, minimum, and maximum values. Categorical data will be reported as frequencies and percentages. Adverse events will additionally be reported as events per subject year, with only those events that start after implantation of the HM II analyzed. The adverse events will be compared between the two arms of the study using risk ratios (Poisson's regression). Survival data will be presented and analyzed using the Kaplan-Meier method.

The primary endpoints will be analyzed per protocol method as defined in **Section 12.1**. Every effort will be made to avoid crossovers, but in such instances, analysis will be performed in accordance with **Section 12.1**. The study will be conducted in a double-blinded fashion with neither the investigator, nor the subject having the knowledge of whether the subject is in the Treatment or the Control Arm. Only the primary statistician from the Sponsor will have knowledge of the specific groups, and all other parties will be blinded.

Every effort will be made to collect all required data. A one-sided 0.025 level of significance or two-sided 0.05 level of significance will be used to declare statistical significance as outlined below. Multiplicity adjustments will not be made unless specified below. A sensitivity analysis will be performed to account for any bias that may have been introduced by subjects withdrawing from the study or being removed from the study.

Clinical Investigational Plan**12.1 STATISTICAL DESIGN, HYPOTHESES, METHOD AND ANALYTICAL PROCEDURES**

Subjects will be block randomized per site on a 1:1 ratio into the Treatment and Control Arms. The study is designed to satisfy two primary endpoints. Both primary endpoints must be met for the study to be successful.

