12.1.3 SAMPLE SIZE

A total sample size of up to 350 subjects will provide adequate power to satisfy both the primary efficacy and the safety endpoints respectively. The assumptions and rationale are provided in the sections below.

Clinical Investigational Plan**12.1.4 PRIMARY EFFICACY ENDPOINT**

Assumptions: Based on the analysis of the first 100 subjects enrolled in the PREVENT study (Data on file), the anticipated incidence of non-surgical bleeding in the Control Arm at 6 months is 40%. The assumption for PREVENT II is that there will at least be a 15% reduction in the incidence of non-surgical bleeding in the Treatment Arm compared to the Control Arm.

The comparison of Treatment and Control Arms will be made using the Fishers Exact Test. The primary endpoint for efficacy will be considered to be met if the p -value ≤ 0.05 . A sample size of 330 subjects (165 in each of the Treatment and Control Arms) with an alpha of 0.05 will provide 80% power to demonstrate a significant difference between the Treatment and Control Arms.

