12.1.5 PRIMARY SAFETY ENDPOINT

Assumptions: Based on the analysis of the first 100 subjects enrolled in the PREVENT study (Data on file), the anticipated composite incidence of TE events in the Control Arm at 6 months is expected to be 8%. The assumption for PREVENT II is that the Treatment Arm will experience an incidence of TE events of no more than 9% at 6 months. The Treatment Arm will be considered non-inferior to the Control Arm if the upper one-sided 95% confidence limit of the risk difference in the 6 month TE rate between research drug arms (Treatment - Control) is less than +10% ("positive 10%", where 10% is the non-inferiority Δ in the above null and alternative hypotheses).

A sample size of 338 subjects (169 each in the Treatment and Control Arms) will achieve 80% power to prove the Treatment Arm is non-inferior to HM II when the margin of non-inferiority is 10% ($=\Delta$ in the above null and alternative hypotheses) using the Farrington-Manning risk difference approach to non-inferiority at a one-sided alpha = 0.025.

[figure not shown]

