12.2.1 PERSISTENT CHANGES TO ANTIPLATELET THERAPY

If the investigator persistently deviates from the CIP by deliberately changing antiplatelet therapy outside of the scenarios outlined above, the subject will be censored from that point onwards. Follow-up will continue, but the data will not contribute to the primary endpoints. This will be considered a CIP deviation and may result in site disqualification. The deviation and details about therapy changes will be recorded on the appropriate CRF.

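### Success requires both primary endpoints, but the plan states 80% power only for each one; at 350 subjects and the planning rates, power to meet both is about 67% under independence, and it is not stated

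*Combined protocol and SAP*

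**What the plan says.** The Synopsis and Section 12.1 set the same success rule: "Both primary endpoints must be met for the study to be successful".

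Power is given one endpoint at a time. For efficacy, Section 12.1.4 says that 165 subjects per arm "with an alpha of 0.05 will provide 80% power to demonstrate a significant difference between the Treatment and Control Arms". For safety, Section 12.1.5 says that 169 per arm "will achieve 80% power to prove the Treatment Arm is non-inferior to HM II when the margin of non-inferiority is 10" per cent. For the total of 350 there is no number, only two general statements. The Synopsis has "A total study sample size of 350 subjects will provide enough statistical power to demonstrate both efficacy and safety" and Section 12.1.3 has "A total sample size of up to 350 subjects will provide adequate power to satisfy both the primary efficacy and the safety endpoints respectively".

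No section gives a power for meeting both endpoints or an assumption about how they depend on each other. No evaluable fraction is stated either. Section 4.2 says "Withdrawn subjects will not be replaced", Section 12 says "The primary endpoints will be analyzed per protocol method as defined in" Section 12.1, and Section 12.2.1 says of persistent deviators that "Follow-up will continue, but the data will not contribute to the primary endpoints".

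**The concern.** When success needs two tests to pass, the power that matters is the probability that both pass. Unless the two results are very strongly positively related, that is clearly lower than either power alone. The plan appears to size each endpoint for 80%, take the larger number and round up, which adds only 6 subjects per arm to the safety requirement. It then describes the total as enough to show both.

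A reader of the Synopsis would naturally take the chance of a successful trial to be about 80%. If it is nearer two in three, a trial that misses one endpoint could be read as stronger evidence against the hypothesis than it is. Requiring both endpoints does not inflate the type I error, so the issue is power only.

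**Working it through.** **Inputs**

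- 350 subjects, 1:1, so 175 per arm (Synopsis).
- Bleeding at 6 months: 40% in Control, with a 15% reduction assumed, tested by Fisher's exact test at 0.05 (12.1.4). The reduction is read as 15 percentage points (25% in Treatment) and the test as two-sided, because that reading reproduces the plan's 165 per arm. A relative reduction (40% vs 34%) would need more than 1,000 per arm.
- Thromboembolic (TE) events at 6 months: 8% Control and 9% Treatment, margin 10 points, Farrington-Manning, one-sided alpha 0.025 (12.1.5).

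**Step 1: reproduce the plan's figures**

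*Efficacy.* Enumerating all outcomes, with rejection when the two-sided Fisher p-value is at most 0.05 and Treatment is lower, gives power 0.805 at 165 per arm. Stated: 80%.

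*Safety.* Power = Φ{[√n × (Δ − δ) − 1.96 × s₀] / s₁}, where:

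- Δ − δ = 0.10 − 0.01 = 0.09
- restricted null rates are 15.45% and 5.45%, so s₀ = √(0.1545 × 0.8455 + 0.0545 × 0.9455) = 0.4269
- s₁ = √(0.09 × 0.91 + 0.08 × 0.92) = 0.3943

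At n = 169: (13 × 0.09 − 1.96 × 0.4269) / 0.3943 = 0.845, and Φ(0.845) = 0.801. Stated: 80%.

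**Step 2: each endpoint at 175 per arm**

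- Efficacy: 0.825, by the same enumeration.
- Safety: (13.229 × 0.09 − 1.96 × 0.4269) / 0.3943 = 0.898, and Φ(0.898) = 0.815. Enumerating the Farrington-Manning test exactly gives 0.828.

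**Step 3: both endpoints**

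- Independence: 0.825 × 0.815 = 0.673. With exact safety power: 0.825 × 0.828 = 0.683.
- Lower bound under any dependence: 0.825 + 0.815 − 1 = 0.640.
- Upper bound: min(0.825, 0.815) = 0.815.
- Within-subject dependence: 400,000 simulated trials per setting used a latent normal correlation between bleeding and TE events, the same in both arms, with exact rejection regions. Joint power was 0.672 at −0.6, 0.682 at 0 and 0.705 at +0.6.

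**Step 4: sensitivity (independence throughout)**

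| Condition | Efficacy | Safety | Both |
|---|---|---|---|
| Planning rates, 175 per arm | 82.5% | 81.5% | 67% |
| TE 8% in both arms | 82.5% | 90.1% | 74% |
| Bleeding 40% vs 23%, TE 8% in both arms | 91.5% | 90.1% | 82.5% |
| One-sided 95% limit in 12.1.5 applied literally (alpha 0.05) | 82.5% | 89.2% | 74% |
| 165 evaluable per arm | 80.5% | 79.1% | 64% |
| 157 evaluable per arm (10% loss) | 78.0% | 77.0% | 60% |

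The last two rows are illustrations, since the documents give no loss rate. For scale only, 80% power for both at the planning rates needs about 215 per arm, or 212 with exact safety power.

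**The case against.** The strongest reply is that nothing stated is numerically wrong. The plan sets 80% per endpoint and never for study success, 350 exceeds both 330 and 338, and Section 12.1.3 makes its claim for each endpoint in turn. That is right for Section 12.1.3. It does not rescue the Synopsis, which claims enough power for both and closes the same entry with the rule that both must be met. The only standard of adequacy the plan offers is 80%.

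Second, the planning rates are a floor for the bleeding reduction and a ceiling for the TE rate, so 67% takes the unfavourable edge of each. This stands. With TE equal at 8% and a bleeding reduction two points larger, joint power passes 80%. But these are the rates at which the plan states its own 80% figures, so they are the right basis for the companion figure.

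Third, 67% multiplies an exact efficacy power by an asymptotic safety power. Exact calculation for both gives 68%, with bounds of 0.825 + 0.828 − 1 = 65% and 82.5%. The difference is immaterial.

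Fourth, the 20 and 12 subjects above the two requirements may be an unstated allowance for loss, and Section 12 plans a sensitivity analysis for withdrawals. The margin covers 12/350 = 3.4% for safety, and the sensitivity analysis addresses bias, not power. The missing evaluable fraction is a gap in detail; the main point does not depend on it.

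Finally, a missed endpoint should be read from its estimate and interval. That is true, but readers also use the stated power, and the one implied here is too high.

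**Conclusion.** The concern holds. The per-endpoint sample sizes are correct, but the Synopsis attributes to 350 subjects a power for the success rule that the plan does not show. At the planning rates the figure is about 67% under independence (68% with exact safety power). It stays at 67% to 70% over the within-subject correlations examined and cannot fall outside 64% to 81.5%. Reaching 80% would need near-maximal positive dependence, which the plan does not claim, or true rates better than those assumed.

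The result rests on four conditions: the 15% reduction is in percentage points, non-inferiority is tested at one-sided 0.025, all 175 per arm are evaluable, and the true rates equal the planning rates. If the one-sided 95% limit in Section 12.1.5 is the rule, the figure is about 74%. Given the plan's rules on withdrawal, per-protocol analysis and deviators, full evaluability is optimistic. At the planning rates, 67% is therefore more likely high than low.

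**What to change.** Keep the sample size. Replace the general power sentences in the Synopsis and Section 12.1.3 with text such as:

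> With 175 evaluable subjects per arm, power is about 82% for the efficacy endpoint (40% vs 25%) and about 82% for the safety endpoint (8% Control, 9% Treatment, margin 10%, one-sided alpha 0.025). Power for study success (both endpoints met) is about 67% assuming the endpoints are independent, and lies between 64% and 81.5% under any dependence.

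Then state the evaluable fraction the sponsor assumes for the per-protocol analysis and give the same three powers at that fraction. Settle first which confidence limit governs non-inferiority. If the one-sided 95% limit in Section 12.1.5 is kept, the figures become about 89% for safety and about 74% for both, and the bounds must be recalculated: 0.825 + 0.892 − 1 = 72% to 82.5%.

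The change is to wording only. Tests, margin and number of subjects are untouched. The cost is a less favourable stated figure.

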2.1 BLEEDING IN HM II PATIENTS

While overall outcomes with the HM II have steadily improved, bleeding and thromboembolic (TE) complications continue to persist (5, 8). In practice, clinicians must balance the risk of bleeding against that of thrombosis by managing patients on chronic antithrombotic therapy, which includes warfarin as well as ASA therapy (14). In HM II patients, the prevalence and incidence of bleeding, particularly gastro-intestinal (GI) bleeding, is elevated and is usually the leading cause of hospital readmissions post-LVAD implant (15, 16).

Antithrombotic therapy in CF-LVAD patients is complicated by the presence of acquired Von Willebrand Syndrome (AVWS) (17-19). In AVWS, patients present with a degradation of high molecular weight (HMW) multimers of Von Willebrand Factor (VWF) protein, which are necessary for platelet binding and normal hemostatic function of the coagulation system. The loss of HMW VWF reduces the ability of platelets to bind to each other, and predisposes patients to bleeding diatheses, including increased rates of GI bleeding (20).

Some investigators have hypothesized that ASA therapy in the presence of AVWS increases the risk of non-surgical bleeding in HM II patients (11). In a single center experience from France, the risk of TE events was not elevated when patients were managed on single antithrombotic therapy (Vitamin K antagonist – Fluindione only, target INR: 2.0-3.0)(11).

These observations led to the design of the TRACE study (Study of Reduced Anticoagulation/Antiplatelet Therapy in Patients with the HeartMate II Left Ventricular Assist System) (Clinical Trials.Gov: NCT01477528), a prospective, multi-center safety study of reduced antithrombotic therapy in HM II patients. TRACE enrolled 200 subjects across the United States and Europe, and demonstrated that HM II patients who were managed without ASA therapy did not experience an increased risk of TE events (12, 13).

Clinical Investigational Plan

The rate of bleeding in the TRACE EU cohort, in particular, appeared to be lower compared to published clinical experience (12, 21).

